5.1 SAFETY PLAN

Ocrelizumab has been recently approved for the treatment of adult patients with relapsing or primary progressive forms of MS in several countries and regions including Australia/New-Zealand, Europe, Middle East, South America and the USA and for the treatment of adult patients in relapsing form of MS in Canada. Identified and potential risks associated with ocrelizumab treatment will continue to be closely monitored throughout the clinical program. Patient safety during the ocrelizumab program is ensured by targeting the most appropriate patient population, stringent safety monitoring by the Sponsor, and protocol-specified ocrelizumab treatment interruption criteria. Patients will be evaluated clinically and with standard laboratory tests before and at regular intervals during their participation in the main study. Safety evaluations will consist of medical interviews, recording of adverse events, physical examinations, and standard laboratory measurements. Adverse events will be graded according to the National Cancer Institute (NCI) CTCAE v5.0.

Administration of ocrelizumab will be performed in a hospital, clinic environment or doctor's office/practice under close supervision of the investigator or a medically qualified staff member with immediate availability of full resuscitation facilities. All adverse events and serious adverse events will be recorded during the study and at 24 and 48 weeks (or until B-cell repletion) after the last dose of ocrelizumab as provided through this study. Safety assessments will include the incidence, nature, and severity of (serious) adverse events graded per the NCI CTCAE v5.0. Safety assessments will be conducted per the schedule of assessments in Appendix 1.

The potential safety issues anticipated in the main study, as well as measures intended to avoid or minimize these issues, are outlined in the following sections.

5.1.1 Risks associated with corticosteroids

The adverse reactions of corticosteroids may result from unwanted glucocorticoid actions, or from inhibition of the hypothalamic-pituitary-adrenal axis. Please refer to local Prescribing Information.

5.1.2 Risks associated with antihistamines

The adverse reactions depend on the sedating properties of the antihistamine and include but are not limited to nausea, drowsiness, headaches, dry mouth, and allergic reactions such as rash. Please refer to local Prescribing Information.

5.1.3 Risks Associated with Ocrelizumab

5.1.3.1 Identified Risks and Adverse Drug Reactions

Infusion-Related Reactions

All CD20+ depleting agents administered via the intravenous route, including ocrelizumab have been associated with acute IRRs. Following the approved administration regimen (which includes the use of premedication prior to treatment with ocrelizumab in order to reduce frequency and severity of IRRs) symptoms of IRRs may occur during any ocrelizumab infusion, but have been more frequently reported during the first infusion. Physicians should alert patients that IRRs can occur within 24 hours of the infusion. Across the RMS and PPMS trials, symptoms associated with IRRs included, but are not limited to pruritus, rash, urticaria, erythema, throat irritation, oropharyngeal pain, dyspnea, pharyngeal or laryngeal edema, flushing, hypotension, pyrexia, fatigue, headache, dizziness, nausea, tachycardia and anaphylaxis.

Patients should be observed for at least one hour after the completion of the infusion for any symptom of IRR. They will be informed about the possibility of delayed post-infusion symptoms and instructed to contact their study physician if they develop such symptoms.

Hypotension, as a symptom of IRR, may occur during ocrelizumab infusions. Therefore, withholding of antihypertensive treatments should be considered for 12 hours prior to and throughout each ocrelizumab infusion.

Further details on prevention and management of infusion-related reactions are described in Section 5.1.4 and in the current IB.

Infections

Infection is an identified risk associated with ocrelizumab treatment, predominantly involving mild to moderate respiratory tract infections. Non-disseminated herpes virus-associated infections, mostly mild to moderate, were also reported more frequently with ocrelizumab (approximately 5 to 6%, simplex and zoster) than with comparators (approximately 3%).

During the controlled period of the pivotal trials, the proportion of RMS patients with serious infections was lower in the ocrelizumab group (1.3%) than in the interferon beta-1a group (2.9%); in PPMS, the proportion of patients with serious infections, was similar in both groups: 6.7% in the placebo group compared with 6.2% in the ocrelizumab group.

Serious, opportunistic, and fatal infections have occurred in patients with lupus and rheumatoid arthritis (RA) treated with ocrelizumab in Phase III clinical trials. Data from completed studies regarding infection risks with ocrelizumab treatment in these patient populations are provided in the Ocrelizumab IB.

No opportunistic infections were reported by any MS patient treated with ocrelizumab during the controlled period of the pivotal trials.

In interventional clinical trials there were no reports of hepatitis B reactivation in MS patients treated with ocrelizumab, but it had been reported in one RA patient treated with ocrelizumab. HBV screening should be performed in all patients before initiation of treatment with ocrelizumab as per local guidelines. Patients with active Hepatitis B Virus should not be treated with ocrelizumab. Patients with positive serology should consult liver disease experts before start of treatment and should be monitored and managed following local medical standards to prevent Hepatitis B reactivation.

Delay ocrelizumab administration in patients with an active infection until the infection is resolved.

For PML see "Potential risks" below.

Decrease in immunoglobulins

Treatment with ocrelizumab resulted in a decrease in total immunoglobulins (Ig) over the controlled period of the studies, mainly driven by reduction in IgM. The proportion of patients with decrease in Igs below LLN increased over time and with successive dosing. Based on additional patient exposure, in cases of continuous decrease over time, a higher risk of serious infection cannot be ruled out.

Serious infections related to decrease in immunoglobulins (particularly in patients previously exposed to immunosuppressive/ immunomodulatory drugs or with preexisting hypogammaglobulinemia)

Based on additional patient exposure an association between decrease in immunoglobulins and serious infections with ocrelizumab treatment was observed and was most apparent for IgG. There was no difference in the pattern (type, type, latency, duration, outcome) of the serious infections reported in this subset of patients compared to the overall serious infections profile. In addition, risk factors for a subset of patients at higher risk of serious infections could not be identified.

Ocrelizumab—F. Hoffmann-La Roche Ltd 67/Protocol MA30143, Version 10.0

Delayed return of peripheral B cells

Treatment with ocrelizumab leads to rapid depletion of CD19+ B cells in blood by 14 days post treatment (first time-point of assessment) as an expected pharmacologic effect. This was sustained throughout the treatment period. The longest follow-up time after the last ocrelizumab infusion from Phase II Study WA21493 in 51 patients, indicates that the median time to repletion (returned to baseline/LLN whichever occurred first) of B cells was 72 weeks (range 27 – 175 weeks).

Impaired Response to Vaccination

After treatment with ocrelizumab over 2 years in pivotal clinical trials, the proportion of patients with positive antibody titers against S. pneumoniae, mumps, rubella, varicella were generally similar to the proportions at baseline.

The results of the randomized, open-label phase IIIb study (BN29739) that assessed if ocrelizumab recipients with RMS raise adequate humoral responses to selected vaccines indicate that patients treated with ocrelizumab were able to mount humoral responses, albeit decreased, to tetanus toxoid, 23-valent pneumococcal polysaccharide, keyhole limpet hemocyanin neoantigen, and seasonal influenza vaccines. The results are summarized in the current version of the IB.

Physicians should review the immunization status of patients being considered for treatment with ocrelizumab. Patients who require vaccination should complete it at least 6 weeks prior to initiation of ocrelizumab. For seasonal influenza vaccines it is still recommended to vaccinate patients on ocrelizumab. Vaccination with live-attenuated or live vaccines is not allowed during treatment and until B-cells have returned to normal levels.

Due to the potential depletion of B-cells in neonates and infants of mothers who have been exposed to ocrelizumab during pregnancy, it is recommended that vaccination with live or live-attenuated vaccines should be delayed until B-cell levels have recovered; therefore, measuring CD19-positive B-cell level, in neonates and infants, prior to vaccination is recommended.

It is recommended that all vaccinations other than live or live-attenuated should follow the local immunization schedule and measurement of vaccine-induced response titers should be considered to check whether individuals can mount a protective immune response because the efficacy of the vaccination may be decreased. Please see IB for further detail.

5.1.3.2 Potential Risks

Progressive multifocal leukoencephalopathy (PML)

PML has been reported in patients receiving ocrelizumab but only in patients where other contributory factors were present, such as prior immunosuppressive treatment (for

Ocrelizumab—F. Hoffmann-La Roche Ltd 68/Protocol MA30143, Version *10.0*

example, natalizumab or fingolimod). Physicians should be vigilant for early signs and symptoms of PML, which can include any new onset, or worsening of neurological signs or symptoms as these can be similar to an MS relapse. If PML is suspected, dosing with ocrelizumab must be withheld. Evaluation of PML, including MRI, confirmatory CSF testing for John Cunningham virus (JCV) DNA and repeat neurological assessments, should be considered. If PML is confirmed, ocrelizumab must be discontinued permanently. Please refer to Appendix 5 for guidance for diagnosis of PML. Please see the IB for more details.

Hypersensitivity reactions

Hypersensitivity may be difficult to distinguish from IRRs in terms of symptoms. A hypersensitivity reaction may present during any infusion, although typically would not present during the first infusion. For subsequent infusions, more severe symptoms than previously experienced, or new severe symptoms, should prompt consideration of a potential hypersensitivity reaction. If a hypersensitivity reaction is suspected during infusion, the infusion must be stopped immediately and permanently. Patients with known IgE-mediated hypersensitivity to ocrelizumab must not be treated.

Malignancies including Breast Cancer

Patients should follow standard breast cancer screening guidelines.

Please see the IB for more details.

Neutropenia

In the controlled treatment period, decreased neutrophils were observed in 12 and 15% of MS patients treated with ocrelizumab, in PPMS and RMS respectively. Most were mild to moderate in severity, approximately 1% of the patients had Grade 3 or 4 neutropenia; and no temporal association with infections was identified. Based on additional patient exposure an association between neutropenia and serious infections with ocrelizumab treatment was not observed.

Additional information can be found in the current IB.

5.1.4 Management of Patients Who Experience Specific Adverse Events

Guidelines for management of specific adverse events are outlined in Table 4. Additional guidelines are provided in the subsections below.

Event	Action to Be Taken
Mild to moderate IRR	 If the event that a patient experiences is a mild to moderate IRR (e.g. headache), the infusion rate should be reduced to half the rate at the time of the event. This reduced rate should be maintained for at least 30 minutes. If tolerated, the infusion rate may then be increased according to the patient's initial infusion schedule.
Severe IRR (or complex of flushing, fever, and throat pain)	 If a patient experiences a severe IRR or a complex of flushing, fever, and throat pain symptoms, the infusion should be interrupted immediately and the patient should receive symptomatic treatment. The infusion should be re-started only after all symptoms have resolved. The initial infusion rate at restart should be half of the infusion rate at the time of onset of the reaction.
Life-threatening or disabling IRR (e.g., anaphylaxis)	 Immediately stop ocrelizumab if there are signs of a life- threatening or disabling IRR during an infusion, such as acute hypersensitivity or acute respiratory distress syndrome. The patient should receive appropriate treatment. Permanently discontinue ocrelizumab in these patients.

Table 4 Guidelines for Management of Specific Adverse Events

hr=hour; IRR=infusion-related reaction

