	Infusion rate (mL/hr)	Max dose per interval (mg)	Cumulative dose (mg)	Infusion rate (mL/hr)	Max dose per interval (mg)	Cumulative dose (mg)	
0-15	100	30	30	40	00.40	00.40	
16-30	200	60	90	40	23.18	23.18	
31-60	250	150	240	85	49.27	72.45	
61-90	300	180	420	130	75.36	147.81	
91-120	300	180	600	169	98.05	245.86	
121 – 215	/	/	/	200	354.14	600	

IRR = infusion-related reaction

Note: Patients will be allowed to switch from the conventional ocrelizumab infusion (~3.5 hours) to the shorter ocrelizumab infusion (~2.0 hours) at any visit after the Week 24 visit, based on the schedules of infusion as per the protocol, after providing written informed consent and in agreement with their treating physician, provided they have not experienced any previous serious IRRs with ocrelizumab treatment. If patients develop a serious IRR while on the shorter infusion, they will be switched to the conventional infusion and should not be restarted on the shorter infusion at any following infusion visit.

Guidelines for dosage modification and treatment interruption or discontinuation are provided in Section 5.1.4.

Any overdose or incorrect administration of study drug should be noted on the Study Drug Administration electronic Case Report Form (eCRF). AEs associated with an overdose or incorrect administration of study drug should be recorded on the AE eCRF.

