4.7 TREATMENT, PATIENT, STUDY, AND SITE DISCONTINUATION

4.7.1 Study Treatment Discontinuation

Patients must discontinue study treatment if they experience any of the following:

- Pregnancy: patients becoming pregnant by chance during the study will be withheld from ocrelizumab treatment, but will remain in trial and will have the opportunity to re-start ocrelizumab treatment after the pregnancy/breastfeeding are over. During pregnancy and breastfeeding, these patients will continue to come for the regular scheduled visits (whenever possible, adhering to the time of scheduled visits as per protocol) and will perform all assessments except MRI. The total duration of treatment period will be 192 weeks from the date of first dose of ocrelizumab, irrespective of how long the treatment was interrupted due to pregnancy.
- Patients who plan to become pregnant during the study will be withheld from ocrelizumab treatment and will follow the recommendations for contraception period after the last infusion with ocrelizumab for at least 6 months or longer in accordance with locally applicable ocrelizumab package leaflet. Upon discontinuation of study treatment, these patients will enter the safety follow-up period but will not restart the study treatment.
- Life-threatening (NCI CTCAE Grade 4) IRR or serious hypersensitivity reaction
- New onset or reactivation of hepatitis B infection
- PML
- Any other serious adverse event, including laboratory values abnormalities, that present an unfavorable benefit-risk of treatment with ocrelizumab as deemed by the investigator.

The primary reason for study treatment discontinuation should be documented on the appropriate eCRF. Patient discontinuing the study treatment prematurely will be further monitored in a safety follow-up (see Section 3.1.4).

Patients who discontinue study treatment prematurely will not be replaced.

Refer to the schedule of activities (see Appendix 1) for details on follow-up assessments to be performed for patients who permanently discontinue study treatment.

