5.3.3 Assessment of Severity of Adverse Events

The adverse event severity grading scale for the NCI CTCAE (v5.0) will be used for assessing adverse event severity. Table 5 will be used for assessing severity for infusion related reactions and adverse events that are not specifically listed in the NCI CTCAE.

Table 5 Adverse Event Severity Grading Scale for IRRs and Other Events Not Specifically Listed in NCI CTCAE

Grade	Severity
1	Mild; asymptomatic or mild symptoms; clinical or diagnostic observations only; or intervention not indicated
2	Moderate; minimal, local, or non-invasive intervention indicated; or limiting age-appropriate instrumental activities of daily living ^a
3	Severe or medically significant, but not immediately life-threatening; hospitalization or prolongation of hospitalization indicated; disabling; or limiting self-care activities of daily living ^{b,c}
4	Life-threatening consequences or urgent intervention indicated ^d
5	Death related to adverse event ^d

NCI CTCAE = National Cancer Institute Common Terminology Criteria for Adverse Events. Note: Based on the most recent version of NCI CTCAE (*v*5.0), which can be found at: ...http://ctep.cancer.gov/protocolDevelopment/electronic_applications/ctc.htm.

- ^a Instrumental activities of daily living refer to preparing meals, shopping for groceries or clothes, using the telephone, managing money, etc.
- ^b Examples of self-care activities of daily living include bathing, dressing and undressing, feeding oneself, using the toilet, and taking medications, as performed by patients who are not bedridden.
- ^c If an event is assessed as a "significant medical event," it must be reported as a serious adverse event (see .Section 5.4.2. for reporting instructions), per the definition of serious adverse event in .Section 5.2.2.
- ^d Grade 4 and 5 events must be reported as serious adverse events (see ...Section 5.4.2. for reporting instructions), per the definition of serious adverse event in ...Section 5.2.2..

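### A disabling but not life-threatening infusion reaction meets two rows of the protocol's management table, with conflicting actions and no rule of precedence

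*Protocol*

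**What the plan says.** Protocol Section 4.3.2.1, after Table 3, makes Section 5.1.4 the operative guidance: "Guidelines for dosage modification and treatment interruption or discontinuation are provided in Section 5.1.4". Table 4 there has three rows, identified by words and not by grade numbers.

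- Mild to moderate IRR: the infusion rate is reduced.
- "Severe IRR (or complex of flushing, fever, and throat pain"): the infusion is interrupted and symptoms are treated. Then "The infusion should be re-started only after all symptoms have resolved", beginning at half the speed in use when the reaction started.
- Third row, headed "Life-threatening or disabling IRR (e.g., anaphylaxis"): ocrelizumab is stopped at once and permanently discontinued.

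Section 5.3.3 says that IRR severity is assessed with Table 5. Grade 3 there reads "Severe or medically significant, but not immediately life-threatening; hospitalization or prolongation of hospitalization indicated; disabling; or limiting self-care activities of daily living". Grade 4 covers life-threatening consequences or a need for urgent intervention and does not mention disability. SAP Section 4.5.2.1 also labels Grade 3 IRRs as severe.

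Among the events that require study treatment to stop, Section 4.7.1 lists "Life-threatening (NCI CTCAE Grade 4) IRR or serious hypersensitivity reaction". The re-treatment criteria in Section 3.1.3 likewise name only a Grade 4 infusion-related event.

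**The concern.** The word *disabling* sits in the severe grade of one table and in the permanent-stop row of the other. An investigator who grades a reaction with Table 5, as instructed, and finds it Grade 3 because it is disabling can then read Table 4 in two ways. Because the reaction is severe, the infusion may be restarted once symptoms resolve. Because it is disabling, the patient receives no more ocrelizumab. Two sites with the same patient could each claim to follow the protocol and do different things. What is at stake is that patient's safety and continued treatment. Section 1.1 of the shorter-infusion substudy protocol (Appendix 10) counts IRRs among the most frequent adverse events of the drug, so the table is in regular use even though the disputed case is rare.

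**Working it through.** No sample-size or power arithmetic applies. The check is a cross-reading of every place that assigns an action to an IRR, using two test cases: (A) an IRR that is disabling and does not meet Grade 4, and (B) a Grade 4 IRR.

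**Step 1: grade case A.** Table 5 is the prescribed scale. *Disabling* is a Grade 3 criterion and not a Grade 4 criterion, so case A is Grade 3. Table 5 and the SAP both call Grade 3 severe.

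**Step 2: apply each rule.**

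| Place | Named IRR trigger | Case A | Case B |
|---|---|---|---|
| Table 4, row 2 | Severe | Met: interrupt, restart at half rate after resolution | Not the row for life-threatening reactions |
| Table 4, row 3 | Life-threatening or disabling | Met: permanent discontinuation | Met: permanent discontinuation |
| Section 4.7.1 | Grade 4 | Not named; reachable only through the item for other serious adverse events, at the investigator's judgement | Treatment must be discontinued |
| Section 3.1.3 | Grade 4 at a previous infusion | Not named | Dosing suspended until resolved, or withheld indefinitely |

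For case B, row 3 and Section 4.7.1 agree, and Section 3.1.3 is compatible with them. For case A, two rows of Table 4 apply together with different outcomes, and the other two lists do not settle which one holds.

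**Step 3: look for a tie-break.** Table 4 gives no grade numbers and no order of precedence. Section 5.1.4 announces further guidelines in subsections, but none follows the table, and the table of contents shows none.

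**Step 4: size.** Section 1.2 gives 291 + 289 = 580 patients randomized in the substudy at its primary analysis. It reports one severe IRR in each group: 2 / 580 = 0.34%. These were laryngeal inflammation and fatigue, and neither is described as disabling. No IRR was serious, life-threatening or fatal, and none led to discontinuation. The overlap is narrower than Grade 3 as a whole: a reaction that is Grade 3 only through hospitalization or limited self-care falls in row 2 alone.

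**The case against.** The strongest reply is that Table 4 escalates, and that a patient who meets the third row gets the third row. That row is the more specific one and is illustrated by anaphylaxis. Row 2 is also conditional, because restart requires all symptoms to have resolved, so a reaction that is still disabling does not qualify. This is a plausible reading, but it is not written down. It also leaves open a reaction that was disabling and then resolved, which satisfies row 2's condition and row 3's heading. Section 5.1.3.1 refers to the Investigator's Brochure as well for IRR management. That document is not available here and could contain a tie-break.

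Three stronger readings may tempt a reader, and the documents do not support them.

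- *That Section 4.7.1 contradicts both rows.* It agrees with row 3 for life-threatening reactions and is compatible with row 2 for an ordinary severe one. It is not stated to be exhaustive, and it includes a discretionary item for other serious adverse events. It fails to resolve the overlap, and that is all.
- *That the hypersensitivity rules conflict.* Section 5.1.3.2 says "If a hypersensitivity reaction is suspected during infusion, the infusion must be stopped immediately and permanently". This concerns the infusion under way, whereas Section 4.7.1 concerns study treatment. Table 4 mentions acute hypersensitivity only as an example of a sign of a row 3 reaction, not as a separate trigger.
- *That the substudy's IRR results depend on which row a site read.* The substudy is complete, and its primary analysis reported no IRR-related discontinuations.

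**Conclusion.** The inconsistency is real and confined to one cell: IRRs that are disabling by Table 5 and do not reach Grade 4. For these, Table 4 supports both a conditional restart at half rate and permanent discontinuation, and the protocol does not say which prevails. Few patients are affected. The documents show no patient in that cell, and severe IRRs of any kind occurred in 2 of 580 substudy patients. No bias in an endpoint is claimed. The point rests on two assumptions: that sites grade IRRs with Table 5 as instructed, and that no document outside those reviewed supplies a precedence rule. It merits correction because the error is in operative safety text, the consequence for an affected patient is large, and the change is small.

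**What to change.** The sponsor should reconcile Table 4 with Table 5 so that every IRR falls in exactly one row. One way is to define the Table 4 rows by Table 5 grade and to state explicitly where a disabling, non-life-threatening reaction belongs. The IRR triggers in Section 4.7.1 and in the Section 3.1.3 re-treatment criteria should then be aligned with the result. Which action applies to such a reaction is a clinical decision for the sponsor, and this review takes no position on it. The cost is a wording change in Table 4 and the two lists, plus a clarification letter to sites. No analysis, sample size or data collection changes.
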